5.3. VISIT WINDOW

Enrolled subjects will attend a total of 3 morning trial visits:

- Visit 1 will be considered Week 1, Day 1 (first day/week of dosing)
- Visit 2 will be performed during Week 13 (± 1 week), 5 days (± 1 day) post-dose
 - If during Week 12, Visit 2 must occur on Days 82 to 84
 - If during Week 13, Visit 2 must occur on Days 89 to 91
 - If during Week 14, Visit 2 must occur on Days 96 to 98
- Visit 3 will be performed during Week 26 (± 1 week), 5 days (± 1 day) post-dose
 - If during Week 25, Visit 3 must occur on Days 173 to 175
 - If during Week 26, Visit 3 must occur on Days 180 to 182
 - If during Week 27, Visit 3 must occur on Days 187 to 189

Subjects <3 years old at Visit 1 will have a total of 4 morning trial visits including the above 3 visits and the addition of:

- C_{max} Visit to be performed during Week 4 (+1 week), 1-2 days after the 4th or 5th dose
 - If during Week 4, C_{max} Visit must occur on Days 23-24
 - If during Week 5, C_{max} Visit must occur on Days 30-31

Post-baseline unscheduled visit (occurred after the date of initiation of the first dose) or end of study visit (early termination visit) will be mapped to the post-baseline scheduled visit with the closest target study day for each scheduled assessment according to [Table 2](#). If the unscheduled visit is in the middle of two scheduled visits, map it to the later one. After mapping, if there are more than one visit in the same window, the visit closer to the target assessment day will be used. If more than one visit has the equal distance to the target day then the later one will be used, if more than one visit on the same day, use the time or the sequence number to select the later record. For listings and shift tables, all data points will be included.

Table 2: Analysis Window

Visit	Screening	Visit 1	C _{max} Visit	Visit 2	Visit 3/ET
Week	Weeks -4 to -1	Week 1	Week 4 (+ 1 Week)	Week 13 (± 1 Week)	Week 26 (± 1 Week)
Target Day		Day 1	Day 29	Day 92	Day 183
Range		Day 1	Day 2 - 60	Day 61 - 137	Day 138 - EOS

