9.6 Dose Adjustments

9.6.1 Dose Adjustment Parameters

The following parameters may be used by the investigator to adjust the TransCon hGH dose without Medical Monitor pre-approval.

At Visit 2, the TransCon hGH dose will be adjusted by the investigator based on weight (See [Section 9.3](#)).

Additionally, the goal for IGF-1 should be between 0 and + 2.0 SDS (unless a different target is identified in consultation with the Medical Monitor). Thus, if the IGF-1 SDS measured at Visit 2 (or the C_{max} Visit, as applicable) is < 0 SDS, and following confirmation of IGF-1 level as < 0 SDS by a second measurement collected 5 days post-dose (± 1 day) at an unscheduled visit, the dose may be increased by approximately 20% to the next higher weight bracket by the investigator (See [Section 9.3](#)).

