14. STATISTICS

14.1 Trial Endpoints

14.1.1 Safety Endpoints

The safety endpoints as measured throughout the 26 weeks of weekly TransCon hGH treatment include the following:

- Incidence of AEs
- Local tolerability, as assessed by the subject/parents/legal guardians/caregivers and the trial staff
- Incidence of antibodies against hGH, including neutralizing antibodies
- Incidence of antibodies against PEG
- Incidence of IGF-1 SDS ≥ 2.0 , ≥ 3.0 with confirmation
- Parameters of HbA1c and lipids
- Hormone levels, including thyroid status and morning cortisol
- All other hematology and chemistry parameters
- Vital sign measurements

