3.3. STUDY ENDPOINTS

3.3.1. Safety Endpoints

The safety endpoints as measured throughout the 26 weeks of weekly TransCon hGH treatment include the following:

- Incidence of AEs
- Local tolerability, as assessed by the subject/parents/legal guardians/caregivers and trial staff
- Incidence of antibodies against hGH, including neutralizing antibodies
- Incidence of antibodies against PEG
- Incidence of IGF-1 SDS >2.0, >3.0 with confirmation
- Parameters of HbA1c and lipids
- Hormone levels, including thyroid status and morning cortisol
- All other hematology and chemistry parameters
- Vital sign measurements

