8. SAFETY ANALYSIS

The safety endpoints ([Section 3.3.1](#)) are measured throughout the 26 weeks of weekly TransCon hGH treatment. These safety variables will be summarized in tables and all safety evaluations will also be listed.

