8.4. IGF-1 SDS

A descriptive table including the number and percentages of subjects by visit will be presented where:

- IGF-1 SDS > 2.0
- IGF-1 SDS > 3.0

Listings of IGF-1 and IGF-1 SDS for subjects with abnormally high IGF-1 SDS will be generated.

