9.3. IGF-1 SDS AND IGFBP-3 SDS

A descriptive table including the frequency and percentages of subjects by each visit will be presented where:

- $0 \leq \text{IGF-1 SDS} \leq 2.0$
- $-2.0 \leq \text{IGF-1 SDS} \leq 2.0$
- $-1.0 \leq \text{IGF-1 SDS} \leq 2.0$
- $\text{IGF-1 SDS} > 2.0$
- $\text{IGF-1 SDS} > 3.0$

The by visit post baseline values and change from baseline in IGF-1 SDS and IGFBP-D SDS will be analyzed by ANCOVA model, including baseline age, peak GH (log transformed) at diagnosis, baseline (of the corresponding variable), prior GH dose level (log transformed), and duration (log transformed) as covariates, and gender as a factor.

The absolute values and change from baseline at each visit of the IGF-1, IGFBP-3, IGF-1 SDS and IGFBP-3 SDS will be also presented with descriptive statistics. Listings will be generated for these outcomes.

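### SAP 5.3 lets an IGF-1 re-test replace the value that triggered it, and no specified table reports the IGF-1 SDS >2.0 / >3.0 endpoint with confirmation

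*SAP*

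**What the plan says.** **Record selection.** SAP 5.3 maps post-baseline unscheduled and early termination visits into the Table 2 windows (target Days 29, 92 and 183). It then states: "After mapping, if there are more than one visit in the same window, the visit closer to the target assessment day will be used". Equal distances go to the later record. The rule is not limited to windows where the scheduled visit is missing. One exception is given: "For listings and shift tables, all data points will be included".

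**Re-tests.** Protocol 9.6.1 allows an IGF-1-driven dose increase only "following confirmation of IGF-1 level as < 0 SDS by a second measurement collected 5 days post-dose", within ±1 day, at an unscheduled visit. Protocol 9.6.2 sets the same timing for values above +2.0 SDS. Both sections refer to values from Visit 2 or the Cmax Visit.

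**Endpoint.** SAP 3.3.1 lists "Incidence of IGF-1 SDS >2.0, >3.0 with confirmation". Protocol 14.1.1 also asks for confirmation but writes the cut-off as "Incidence of IGF-1 SDS ≥ 2.0". SAP 8 says of the 3.3.1 endpoints: "These safety variables will be summarized in tables and all safety evaluations will also be listed".

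**Analysis.** SAP 8.4 reads "A descriptive table including the number and percentages of subjects by visit will be presented where", followed by the cut-offs >2.0 and >3.0. SAP 9.3 repeats those counts beside the normal-range categories, and adds an ANCOVA of "The by visit post baseline values and change from baseline in IGF-1 SDS". Table 3 in SAP 5.4 has no variable for a confirmed elevation.

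**The concern.** There are two linked problems.

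1. The extra records that Protocol 9.6 creates are not a random sample. They follow out-of-range values, whereas in-range values are not re-tested. If the re-test is nearer the target day, the out-of-range value leaves the by-visit tables and the ANCOVA. Regression to the mean then moves those outputs toward 0 to +2.0 SDS at Visit 2 and the Cmax Visit. Unscheduled visits for other reasons (Protocol 10.2.3) can also displace values, but the selective shift comes from these re-tests.

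2. Confirmation needs two values from the same subject. The by-visit tables hold one record per window, and the first value and its re-test normally share a window. The primary objective is safety, and one of the listed safety endpoints has no derivation for either threshold, by visit or over the trial. Its definition is left to whoever programs the tables.

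**Working it through.** **Reproducing Table 2.** The window limits are midpoints of the target days: (29 + 92)/2 = 60.5 and (92 + 183)/2 = 137.5. These give Days 2-60, 61-137 and 138 to end of study, as printed. Dose *k* falls on Day 1 + 7(*k* − 1), so dose 12 is on Day 78. Adding 4-6 days gives Days 82-84, the Week 12 Visit 2 days in SAP 5.3. The other permitted days agree in the same way.

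**Applying the rule.** A re-test on Day *r* replaces a scheduled value on Day *s* when |*r* − target| ≤ |*s* − target|; equality counts because ties go to the later record. Every permitted scheduled day was paired with every later day lying 4-6 days after a dose.

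| Scheduled value | Days from target | Re-test | Pairs replaced |
|---|---|---|---|
| Visit 2, Week 12 (Days 82-84) | 8-10 | Weeks 13-14 (Days 89-91, 96-98) | 18 of 18 |
| | | Week 15 (Days 103-105) | 0 of 9 |
| | | same dose | 3 of 3 |
| Visit 2, Week 13 (Days 89-91) | 1-3 | Week 14 | 0 of 9 |
| | | same dose | 3 of 3 |
| Visit 2, Week 14 (Days 96-98) | 4-6 | any | 0 |
| Cmax Visit, Week 4 (Days 23-24) | 5-6 | after dose 4 (Days 26-28) | 6 of 6 |
| | | after dose 5 (Days 33-35) | 5 of 6 |
| | | after dose 6 (Days 40-42) | 0 of 6 |
| Cmax Visit, Week 5 (Days 30-31) | 1-2 | any | 0 |

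The one dose-5 pair that is kept is Day 24 against Day 35 (5 days from target against 6).

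**Turnaround.** No laboratory turnaround is stated. Same-dose Visit 2 re-tests need result, recall and redraw within 1-2 days and are unlikely. Dose-4 re-tests after a Week 4 Cmax Visit need 2-5 days. The realistic routes are 5-9 or 12-16 days after a Week 12 Visit 2, and 9-12 days after a Week 4 Cmax Visit.

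**Week 26.** An unscheduled record on Days 138-172 is at least 183 − 172 = 11 days from target. An on-time Visit 3 (Days 173-189) is at most 183 − 173 = 10 days away, so the Visit 3 value is kept. Protocol 10.2.3 places unscheduled visits between scheduled ones, and 10.2.5 has no routine follow-up after Visit 3, so a later record is not expected.

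**Do the two values share a window?** The latest on-time Visit 2 is Day 98, and 137 − 98 = 39. The latest on-time Cmax Visit is Day 31, and 60 − 31 = 29. A re-test within 39 or 29 days respectively is therefore in the same window as the value it should confirm, and only one of the two is tabulated.

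**Size (illustration only; none of these inputs is in the documents).** Take first value and re-test as bivariate normal with mean 0.5 to 1.5, total SD 1.2, within-subject SD *w* = 0.3 to 0.6 and correlation 1 − *w*²/1.44 (0.94 to 0.75). Assume one third of Visit 2s are in Week 12 and re-tests fall in Weeks 12-14. The gain in the Visit 2 share at 0 to +2.0 is 1/3 × uptake × P(first value out of range, re-test in range).

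- No re-tests: 0 points.
- All values >+2.0 re-tested: (2.6 to 10.4)/3 = 0.9 to 3.5 points; half of them re-tested, 0.4 to 1.7.
- All out-of-range values re-tested: (7.7 to 15.8)/3 = 2.6 to 5.3 points.

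At mean 1.0, a single value exceeds 2.0 with probability 1 − Φ(1/1.2) = 20.2%, and both values do with probability 12.2 to 16.3%. For 3.0 the figures are 1 − Φ(2/1.2) = 4.8% and 2.1 to 3.4%.

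**The case against.** The case for leaving the plan alone has several parts.

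- *Closest-to-target selection is pre-specified and reproducible, in a single-arm trial with descriptive or covariate-adjusted summaries.* True, and it limits the harm. But a reproducible rule can still select on the outcome.
- *The efficacy endpoints are at 26 weeks, and a Visit 2 replacement is itself 5 ±1 days post-dose.* Both points stand. A reader might infer that the Week 26 normalization result is biased, but the windows do not support that when a Visit 3 value exists.
- *The Cmax Visit route concerns only children under 3, a cohort with no pre-set size, and their endpoint is defined at 1-2 days post-dose.* This also stands. That endpoint is exposed only if it is programmed by visit window rather than by actual post-dose time.
- *Confirmation is described in Protocol 9.6.2, and the listings keep every value.* Section 9.6.2 is a dosing step for values above +2.0. It does not mention 3.0 and does not define an incidence. Confirmed cases could be found by hand in the listings, but SAP 8 promises tables, and IGF-1 is not among the SAP 8.5 parameters that have shift tables.
- *SAP 5.4 lets programmers add variables.* It exempts from amendment only variables unrelated to the primary or key secondary targets. Safety is the primary objective.

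The two effects also partly offset each other. Where a re-test replaces a value above 2.0, the subject stays in the >2.0 count only if the re-test is also above 2.0. That moves the table toward the confirmed count.

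**Conclusion.** Both parts hold, with different weight.

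The missing derivation is the substantive one. The specified tables do not report the endpoint that SAP 3.3.1 names, and this conclusion rests on no distributional assumption. A reader might go further and say that the tables would overstate the endpoint. That follows only within a visit, where the single-value count is at or above the confirmed count. The endpoint covers the whole 26 weeks. If elevations can be confirmed at more than one visit, subjects confirmed at different visits add up, and the total can exceed any single column. No direction can be stated for an incidence over the trial.

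The precedence gap is minor. The reading of the rule is firm: 18 of 18 day pairs for a Week 12 Visit 2 with Week 13-14 re-tests, and 5 of 6 for a Week 4 Cmax Visit with dose-5 re-tests. The effect on results depends on visit timing, laboratory turnaround and re-test uptake, which the documents do not give. It may be small or zero; the 0 to 5.3 points above only illustrate it.

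The difference between ≥ in the protocol and > in the SAP is a separate small inconsistency in the same endpoint.

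**What to change.** **SAP 5.3.** For by-visit summaries and models, use the scheduled-visit record. Use an unscheduled record only if the scheduled one is missing and, for IGF-1, only if it lies in that visit's post-dose window (1-2 days for the Cmax Visit, 5 ±1 days for Visits 2 and 3). With this precedence no pair in the table above is replaced. Target days need no change.

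**SAP 8.4.** Add, for analysis only, one subject-level table over all post-baseline values, for >2.0 and for >3.0, with four rows: any value, confirmed, not confirmed, no re-test available. Count an elevation as confirmed when an unscheduled re-test exceeds the same threshold and was taken:

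- 5 ±1 days post-dose;
- after the index sample;
- before the next scheduled visit and before any change of dose.

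A later scheduled visit does not count as a re-test. Otherwise Visit 3, about 13 weeks later and possibly after a dose change, could confirm or refute a Visit 2 elevation. Elevations without a qualifying re-test, including most at Visit 3, go in the last row. A re-test drawn after a weight-bracket change made at Visit 2 would not qualify, so a footnote should give the number of such cases.

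**Cut-off.** Reconcile ≥ in Protocol 14.1.1 with > in SAP 3.3.1 and 8.4.

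The cost is SAP wording and one table. No new data are needed, and no dosing or clinical rule changes.

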5.4. DERIVED AND COMPUTED VARIABLES

[Table 3](#) provides the rules for derived and computed variables which have been initially identified as important for the analysis of the safety, efficacy or PK/PD as appropriate. It is expected that additional variables will be required. The SAP will not be amended for additional variables that are not related to the primary target or key secondary target variables. Any additional derived or computed variables will be identified and documented in the SAS programs that create the analysis files.

The birth date for each subject is collected on the eCRF. To be consistent with all the other TransCon hGH studies, the 15th day of the reported month is used to calculate the age and related scores. In such case, all the height SDS for the subjects will be calculated using 15th as the birth day. The HSDS reported in the eCRF will not be used as it is based on the actual birth date reported by the subject. FMD K&L will utilize the published SAS macro to calculate the height SDS and no independent QC is required for published SAS macro.

Table 3: Parameter Definition

Parameter	Definition
Annualized Height Velocity at visit x (HV) cm/year	$((\text{Height (Visit } x) - \text{Height (Visit } 1)) * 365) / (\text{Date (Visit } x) - \text{Date (Visit } 1))$
Height Standard Deviation Score (HSDS)	Height SDS will be derived using CDC 2000 (United States of America). A standard SAS program is published at: https://www.cdc.gov/nccdphp/dnpao/growthcharts/resources/sas.htm
Change from baseline over 26 weeks	The value of each variable at each post-baseline time point minus the baseline score.
Normalized serum IGF-1 SDS	Proportion of subjects with IGF-1 Standard Deviation Score (SDS) of 0 to +2.0. Also derive for -2.0 to +2.0, -1.0 to +2.0.
Parents' Height SDS	$((\text{Parents Height}/M)^L - 1) / (L * S)$ Where M=median, S= generalized coefficient of variation, and L= power in the Box-Cox transformation, the M, S, L values are obtained from the CDC website; Percentile Data Files with LMS Values
Total Duration of Treatment (day)	Last treatment date – first treatment date +7
Total Duration of Treatment (week)	Round (Total Duration of Treatment in days/7) to the nearest integer
Treatment Compliance	Total Number of Dose Taken/Total Duration of Treatment (week)

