8.2 Premature Subject Withdrawal

Early withdrawal occurs when an enrolled subject ceases participation in the trial, regardless of the circumstances, prior to the expected completion of the trial. Additionally, the investigator may discontinue the treatment of a subject at any time if considered to be in the subject's best interest. Unless informed consent is withdrawn, any subject who discontinues treatment should be encouraged to remain in the trial and attend all subsequent clinic visits. See [Section 7.3.1](#) for a list of stopping rules governing early termination of subjects from the trial.

In the case of premature discontinuation of a subject's participation in the trial (eg, withdrawal of informed consent), the investigator should schedule an Early Termination Visit to collect data, particularly AE follow-up data (if applicable), and to collect blood for laboratory evaluations. This visit should contain all assessments from Visit 3 (Week 26), and should be documented in the eCRF together with the reason(s) for trial discontinuation. In the case of treatment discontinuation for causes other than withdrawal of informed consent, subjects should be urged to remain in the trial and attend all subsequent trial visits. An Early Termination Visit is not required for subjects who remain in the trial after discontinuing study drug. However, if the subject is not willing to attend all subsequent trial visits, this should be considered a withdrawal from the trial and an Early Termination Visit should be scheduled.

Every effort should be made to observe subjects who have received at least 1 dose of study drug for the entire observation period, even if they discontinued trial treatment. The investigator should make every attempt to contact the subject/parent/legal guardian via phone to arrange the appropriate follow-up assessment(s) for such subjects.

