9.5 Selection of Trial Doses

TransCon hGH is an inactive prodrug. The phase 2 pediatric GHD trial with TransCon hGH demonstrated that a dose of 0.21 mg hGH/kg/week provided similar hGH exposure, efficacy (annualized HV), and safety/tolerability compared to the equivalent weekly dose of Genotropin, with PD demonstrating normalization of IGF-1 SDS. This trial also demonstrated comparable tolerability and safety and numerically greater annual HV with a 0.30 mg/kg/week dose of TransCon hGH. Treatment guidelines support initiation of hGH at a dose of 0.24 mg hGH/kg/week ([Grimberg 2016](#)). The TransCon hGH 0.24 mg hGH/kg/week dose is currently being studied in the phase 3 heiGHt Trial. To align the starting dose across the TransCon hGH program, the same dose has been chosen for the current trial. Given non-compliance rates on daily hGH doses versus the expected increased compliance in this trial, even subjects entering on 0.30 mg hGH/kg/week will likely do well on the lower TransCon hGH dose. Importantly, IGF-1 levels, along with other safety parameters discussed in [Section 9.6](#), will be measured at Visit 2 (and the C_{max} Visit, as applicable) and, if needed, changes in dosing allowed.

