10.2 Trial Periods and Visits

Following the Screening Period, enrolled subjects will attend a total of 3* morning trial visits:

- **Visit 1:** Week 1, Day 1 (1st week/day of dosing)
- **Visit 2:** Week 13 (±1 week), 5 days (±1 day) after the 12th, 13th or 14th dose
- **Visit 3:** Week 26 (±1 week), 5 days (±1 day) after the 25th, 26th or 27th dose

* All subjects < 3 years old at Visit 1, will also have the following morning visit:

- **C_{max} Visit:** Week 4 (+1 week), 1-2 days after the 4th or 5th dose

All visits should be in the morning for consistent height measurements. Attempts should be made to adhere to the planned visit schedule. It is suggested that the site staff provide dosing, diary, and visit reminders (eg, phone calls) to subjects/parents/legal guardians between visits.

An overview of all visits is provided in the Schedules of Events ([Section 18.2](#)).

For detailed descriptions of assessments refer to [Section 11](#).

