8.7. EXPOSURE AND COMPLIANCE

Summary tables will be presented for the following variables:

- Total duration of treatment
- Total number of actual doses
- Total actual dosage (mg)
- Compliance rate

The dosage (mg) is the product of the dose volume (mL) and dose concentration (mg/mL) reported in the eCRF. When there are three or more observed consecutive doses with more than 15% difference between actual dose and expected dose (0.24mg/kg/week), it will be considered as a dose reduction/increase. The frequency and percentages of subjects for dose not changed, dose increased or decreased will also be summarized by visit.

The compliance rate will be calculated based on the rules in [Section 5.4](#). Compliance rate will be summarized using the following categorization; <80%, ≥80%, ≥90%, ≥95% and 100%.

Listings will be presented for all exposure information.

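### The compliance denominator ends one week after the last injection taken, so a child who stops injecting for good scores 100% whatever the week

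*SAP*

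**What the plan says.** Three lines of SAP Table 3 (section 5.4) fix the compliance rate:

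- Compliance is "Total Number of Dose Taken/Total Duration of Treatment (week").
- Duration in days is "Last treatment date – first treatment date +7".
- Duration in weeks, the denominator, is "Round (Total Duration of Treatment in days/7) to the nearest integer".

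SAP section 8.7 applies this rule to the exposure tables: "The compliance rate will be calculated based on the rules in" section 5.4. It then groups subjects at cut points of 80%, 90% and 95%, with 100% as the top category.

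Protocol section 9.8 bases compliance on drug accountability and diary review but gives no formula. Neither document puts scheduled doses, the Visit 3 date or the end-of-study date into the denominator.

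Two other protocol provisions matter. Section 8.2 says that, unless consent is withdrawn, "any subject who discontinues treatment should be encouraged to remain in the trial". Section 10.2 places Visit 3 at "Week 26 (±1 week), 5 days (±1 day) after the 25th, 26th or 27th dose".

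**The concern.** A compliance rate should compare the doses taken with the doses that were due. Here the child's own last injection sets the denominator. A gap between two injections counts as missed doses, but an unbroken run of missed doses after the last injection counts for nothing. The rate therefore depends on when doses were missed as well as on how many.

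The children concerned are foreseeable, because the protocol asks those who stop drug to keep attending. Cutting the denominator short can only raise the rate, and it raises it most for those who stopped earliest.

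The stake is modest but not empty. Protocol section 9.5 supports the choice of dose partly by expected compliance: "Given non-compliance rates on daily hGH doses versus the expected increased compliance in this trial". Section 5.5 expects better compliance from dropping daily injections. The one planned compliance rate should be able to show a child who gave up injecting.

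**Working it through.** The documents state no compliance figure to reproduce, so the check applies the Table 3 rules to weekly schedules.

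**Inputs.** The three formulas come from SAP Table 3. Doses fall weekly on Days 1, 8, ..., 176. By Visit 3, 26 doses are due, with 25 or 27 if the visit falls a week early or late (protocol section 10.2).

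**Full course.** First dose Day 1, 26th dose Day 176. Days = 176 − 1 + 7 = 182; weeks = 182/7 = 26; compliance = 26/26 = 100%. The rule works for a child who completes dosing.

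**Stopping for good after k consecutive weekly doses.** Days = 7(k − 1) + 7 = 7k; weeks = k; compliance = k/k = 100% for every k.

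| Doses taken, then none | SAP rule | Of 26 due | Range (27 to 25 due) |
|---|---|---|---|
| 4 | 100% | 15.4% | 14.8% to 16.0% |
| 10 | 100% | 38.5% | 37.0% to 40.0% |
| 13 | 100% | 50.0% | 48.1% to 52.0% |
| 20 | 100% | 76.9% | 74.1% to 80.0% |
| 22 | 100% | 84.6% | 81.5% to 88.0% |

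**Same number missed, different position** (26 due).

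- Four missed mid-trial: 22/26 = 84.6%. Four missed at the end: 22/22 = 100%.
- Six missed mid-trial: 20/26 = 76.9%. Six missed at the end: 20/20 = 100%.

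Against 26 due, two doses missed at the end (24/26 = 92.3%) already fall below 95%, three (23/26 = 88.5%) below 90%, and six (76.9%) below 80%. The SAP rule reports all of them as 100%.

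**Who is unaffected.** A child still dosing and seen in window had the last injection 4 to 6 days before Visit 3. The denominator then covers the whole period, and every earlier miss is counted.

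**Meaning of last treatment date.** The SAP does not define it. If it meant the Visit 3 date, say Day 181, days = 181 − 1 + 7 = 187, weeks = round(26.7) = 27, and a child with all 26 doses would score 26/27 = 96.3%. The added seven days make sense only if the date is that of the last injection.

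**Rounding.** This is a separate and smaller effect, and it runs both ways. For 26 doses over 178 days, round(25.43) = 25 and 26/25 = 104%. Over 186 days, round(26.57) = 27 and 26/27 = 96.3%. Leaving weeks unrounded would not remove values above 100%: 26/(178/7) = 102.2%. A rate above 100% has no place in the listed categories.

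**Effect on the summary.** The number of children who will stop is unknown before the data, so no total can be given. With 150 children in the table, each one who stops after 20 of 26 doses raises the mean rate by (100 − 76.9)/150 = 0.15 percentage points. Each one who stops after 4 raises it by (100 − 15.4)/150 = 0.56 points.

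**The case against.** The best defence is that adherence while on drug and persistence on drug are different quantities, and the SAP has chosen the first. Protocol section 9.6.2 lists grounds on which the investigator or Medical Monitor may stop study drug, and doses withheld on instruction are not non-compliance. That stands. For those children an on-treatment denominator is reasonable, and the fix keeps it. It does not cover a child who was still meant to be dosing and quit, and the SAP does not label its rate as on-treatment.

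A reader might infer that early stopping is hidden. It is not. SAP section 8.7 also tabulates treatment duration, number of doses and total dosage, and lists all exposure data. Section 8.1 covers adverse events leading to drug discontinuation, and section 6.1 covers leaving the trial. A child who stops for a reason other than an adverse event and keeps attending is in neither of the last two. The duration and dose counts would show the short course, but they do not correct the compliance categories.

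A reader might also infer that every late missed dose is lost, or that every feature of the rule flatters the product. The Visit 3 window rules out the first for children still dosing, and the rounding examples rule out the second. Only the shortened denominator has a fixed direction.

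**Conclusion.** The point holds within limits. For a child who stops injecting but remains in the trial, or who skips the final injections, Table 3 discards the missed doses and returns 100%. At 20 doses the overstatement is 23.1 percentage points against 26 due, or 20.0 to 25.9 points for 25 to 27 due. With 25 due the correct rate is exactly 80.0%, so whether that child should move to the category below 80% depends on when Visit 3 falls.

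This rests on two assumptions: that last treatment date means last injection, which the added seven days support, and that doses are due weekly up to Visit 3. The subject-level error then follows by arithmetic. Its total effect depends on how many children stop, which the documents cannot tell us.

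It would be wrong to conclude that the trial's findings are at risk. Compliance is not among the endpoints in either document, there is no concurrent daily-treatment arm, and nothing is tested on it. No endpoint, test or sample size changes. It is still worth correcting, because the rule as written errs in a known direction and is cheap to change.

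**What to change.** In SAP Table 3:

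1. Define compliance as doses taken divided by the whole number of weekly doses due from the first dose to Visit 3 or the early termination visit. End the count earlier only at a documented stop directed by the investigator or Medical Monitor.
2. Where the reason for stopping drug is not recorded, count the doses due to Visit 3 or early termination. This default is needed because the documents show no field for the reason when a child stops drug but stays in the trial.
3. Define last treatment date as the date of the last injection.
4. Keep the present ratio only as a secondary rate, labelled 'while on treatment'.

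In SAP section 8.7, make the top category 100% or more, so that every value has a place.

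The cost is one extra derivation and a few lines of SAP text. Injection dates are in the diary, and visit dates are already needed for height velocity. The reported compliance may come out slightly lower.
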